  - 3. A minimum of three attempts at contact should be made for both the reminders to return kits and access test results. If a participant does not respond to these attempts, the project coordinator can make additional attempts for the duration of the study unless the participant explicitly asks to no longer be contacted.
- (b4) Overview of the Contact and Retention Protocol for monthly raffles:
  - 1. Each month participants will be sent an email with a link to enroll in a \$50 raffle. These monthly raffles will serve to confirm that a participant's email address is up to date and in use.
  - 2. If a participant does not click the raffle link within 48 hours, the project coordinator will make at least three attempts to call the participant to confirm that the email address is up to date and in use. If the participant is not reached within a week, the project coordinator will contact approved alternative contacts (e.g., parent, friend). In addition, project coordinators will utilize Internet,

- public database systems, and private services to locate any individual who is unresponsive to contact efforts.
- 3. Participants will be contacted for the duration of the study unless they express their intention to withdraw from the study.
- (c) Intervention delivery. Upon enrollment, participants will randomly assigned by the online program to receive KIU! or the HIV knowledge control arm. Randomization will be stratified by race and CBO at baseline by computerized system. Stratifying by race will assure sufficient representations by race/ethnicity in each condition to address Aim 3—exploring potential racial/ethnic differences in outcome effects. Stratification by CBO will prevent imbalance in factors that may influence intervention responsiveness across cities and clinics. After the pre-test assessment and remote STI testing, participants will receive the intervention content across three sessions across a minimum of 3 days and a maximum of 3 weeks, based on principles of effective HIV interventions and high acceptability in the pilot phase (see preliminary studies). The existing booster session will be delivered at 3 months, and the newly created booster session content at 3 and 6 months.

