The primary behavioral outcome measure of treatment success will be the count of unprotected anal sex acts and the biomedical endpoint will be NG/CT incidence (Aim 2). Secondary outcomes include: condom errors, IMB factors, and receipt of an HIV test. We will also explore intervention effects separately for receptive and insertive anal sex. The primary independent variable of interest is the indicator for the intervention group. The baseline value of the outcome and other required covariates at baseline will be included as additional independent variables. The intervention will recruit participants from multiple sites (multiple clinics in three cities); however it is not delivered in groups so site will be adjusted for as a fixed rather than a random independent variable. A random intercept term will be included to account for individual average levels of the outcome. The effect of time will first be estimated as a categorical variable in order to describe and adjust for time trends as observed. A second strategy will start with estimating a single slope reflecting average change across all 4 time points, then add a guadratic term if it contributes significantly to the model. Random effects for time variables, reflecting individual variations in time trends, will be included in addition to random intercepts, if significant. A single effect of group will test the intervention effect averaged across all time points, adjusting for all included covariates and underlying time trends. Potential moderators (race/ethnicity, relationships status, and gay/bisexual identity) will be added as independent variables and their interactions with intervention group will be tested (Aim 3). Addition of interaction terms between time and intervention group will provide a test for comparing time trends in change scores between groups.

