YMSM will participate in either usability and acceptability tests in phase 1 or the RCT in phase 2. In phase 1 (months 1-6), we will perform necessary technological upgrades to the tracking system, program additional booster modules, conduct usability testing, and prepare for the RCT. Twelve ethnically diverse YMSM (4 Caucasian, 4 African American, 4 Latino) will participate in usability and acceptability testing of new booster session and the existing modules that will be updated with video interviews conducted in New York and Atlanta. A testing protocol established by the Northwestern University Center for Behavioral Intervention Technologies (CBIT) will be used to assess usability across standards (i.e. across different monitors, bandwidths, etc.) and in practice with target participants who will "think out loud" and be observed as they go through the modules (i.e. ability to navigate, cultural appropriateness). Participants in usability testing will be reimbursed \$35 in cash for approximately 90 minutes of their time and for travel expenses.

In phase 2 (months 7 – 48), 4500 YMSM will participate in the RCT phase of the study. About 20% of these young men (n = 900) are anticipated to enroll into and complete the study. Participants will be automatically randomized into the experimental intervention (KIU!) or the control condition (HIV Knowledge) after verification of participant eligibility and completion of informed consent online. Randomization will be stratified by race and recruitment clinic. In both arms of the trial we will test for Gonorrhea (NG) and Chlamydia (CT), using the athome rectal swab test kits and at-home urine test kits, and refer for treatment as necessary at baseline and post-intervention. In the experimental condition, participants will have already received HIV testing and counseling, and in the context of the proposed study will receive the highly-interactive and YMSM-tailored Internet-based prevention program called Keep It Up! (KIU!). Consistent with meta-analytic data on effective HIV interventions, the content will be delivered over three sessions across a three week period (see Appendix

1 for intervention overview). Participants in the KIU! arm will also receive booster sessions at 3- and 6--months from completion of the intervention. These sessions continue to provide HIV prevention motivation and behavioral skills training.

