This is a two-group, active-control, RCT of an online intervention. The study's hypothesis concerns betweengroup differences in the change in HIV/STI risk behavior and STI incidence from pre-intervention to later followups. There are 4 assessment points of RCT outcomes: baseline, 3, 6, and 12 months post-intervention. Prior to conducting full analyses, standard descriptive analyses will be conducted to check for invalid values, outliers, and logical consistency between variables. We will assess the comparability of the experimental and control groups at baseline. If any variables differ significantly at baseline, they will be included as covariates in the adjusted outcome analyses along with variables known from prior research (e.g. age) to be correlated with the outcome under analysis. Following extensive data description and analysis at separate follow-up points, the primary analysis will utilize all follow-up points by fitting mixed effect regression models. Also known as hierarchical linear models (HLM) ²⁰⁵⁻²⁰⁷, these models allow for the presence of missing data, time-varying or invariant covariates, and subject measurement at different time points. HLM models appropriate to the characteristics of the distribution (i.e. normal, Poisson) will be fit using SAS.

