The primary behavioral outcome measure of treatment success will be the count of unprotected anal sex acts and the biomedical endpoint will be NG/CT incidence (Aim 2). Secondary outcomes include: condom errors, IMB factors, and receipt of an HIV test. We will also explore intervention effects separately for receptive and insertive anal sex. The primary independent variable of interest is the indicator for the intervention group. The baseline value of the outcome and other required covariates at baseline will be included as additional independent variables. The intervention will recruit participants from a variety of sources. Participants will be recruited (1) from the testing clinics and mobile testing units of our partner CBOs in Chicago, New York, and Atlanta, (2) using print, online, and recorded ads, (3) by referral from ongoing studies and IRB-approved research participant registries at the university sites, and (4) by referral from community partners who provide HIV testing. Regardless of recruitment source, prior to beginning the intervention, participants will still have the contact with an HIV testing counselor or study team member that is important for recruitment and retention. However it is not delivered in groups so site will be adjusted for as a fixed rather than a random independent variable. A random intercept term will be included to account for individual average levels of the outcome. The effect of time will first be estimated as a categorical variable in order to describe and adjust for time trends as observed. A second strategy will start with estimating a single slope reflecting average change across all 4 time points, then add a quadratic term if it contributes significantly to the model. Random effects for time variables, reflecting individual variations in time trends, will be included in addition to random intercepts, if significant. A single effect of group will test the intervention effect averaged across all time points, adjusting for all included covariates and underlying time trends. Potential moderators (race/ethnicity, relationships status, and gay/bisexual identity) will be added as independent variables and their interactions with intervention group will be tested (Aim 3). Addition of interaction terms between time and intervention group will provide a test for comparing time trends in change scores between groups.

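### The primary model's covariates are not closed in advance: beyond the baseline outcome and site they enter by baseline significance tests or open wording, and race, a randomisation stratum, is not required

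*SAP*

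**What the plan says.** SAP C3 and Protocol B.11 give the same covariate rules.

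- By test: "If any variables differ significantly at baseline, they will be included as covariates in the adjusted outcome analyses". Neither the variables to be tested nor the test level is given.
- By prior knowledge, in the same sentence: "along with variables known from prior research (e.g. age) to be correlated with the outcome under analysis". Age is the only example.
- By name, plus an open phrase: "The baseline value of the outcome and other required covariates at baseline will be included as additional independent variables". The other required covariates are not listed.
- Site: "site will be adjusted for as a fixed rather than a random independent variable".

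These rules reach the primary test: "A single effect of group will test the intervention effect averaged across all time points, adjusting for all included covariates".

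On the design side, Protocol B.10(c) and SAP B.3.a.1 say "Randomization will be stratified by race and CBO at baseline by computerized system", and Protocol C.1.a says "Randomization will be stratified by race and recruitment clinic". In the analysis sections race appears only under Aim 3: "Potential moderators (race/ethnicity, relationships status, and gay/bisexual identity) will be added as independent variables", with their interactions with arm. The power sections (Protocol B.12, SAP A.5) expect some extra power from adjusting for the blocked design, but do not say which terms would do this.

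**The concern.** Two analysts who follow the text could fit different primary models. One might take age and race as known predictors. Another might take age only and add whatever happened to differ at baseline. The missing-data assumption (Protocol B.11, SAP C3) is conditional on the variables in the model, so it is left open as well.

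The significance test is a poor way to fill the gap. After correct randomisation, a significant baseline difference is a chance event and says nothing about whether the variable predicts the outcome. For race the rule is close to empty, because stratification balances race by design. A stratum that shapes the randomisation may therefore be missing from the primary model, with a standard error that is slightly too large. What is at stake is a fixed, reproducible primary analysis and a little precision.

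**Working it through.** The plan attaches no figure to its covariate rule, so there is none to reproduce. The checks below ask how often the model would change by chance, whether the test size is affected, and what omitting race costs.

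**1. Chance selection.** With k independent baseline variables tested at 5% (k and the level are assumptions), the chance that at least one is selected is 1 − 0.95^k:
- k = 5: 22.6%
- k = 10: 40.1%
- k = 20: 64.2%

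**2. Type I error of the rule applied mechanically.** Linear approximation. Let Zx be the imbalance statistic and r the correlation of the variable with the outcome, given the covariates always in the model. Under the null:
- unadjusted Zu = r·Zx + √(1−r²)·e
- adjusted Za = (Zu − r·Zx)/√(1−r²)

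The rule uses Za if |Zx| > 1.96, otherwise Zu. Simulated type I error is 5.0%, 4.9% and 4.8% for r = 0.1, 0.2 and 0.3. With 5 or 10 variables at r = 0.1 each it is 4.9% or 4.7%. There is no inflation.

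**3. Would the rule select race?** Inputs: 900 men, three race groups, and either 11 CBOs (counted from SAP B.1) or 18 sites (assumed). Permuted blocks of 2, 4, 6 or 8 were drawn within race-by-site strata; the block size is assumed because the documents do not give it. Race by arm was significant at 5% in 0 of 4,000 randomisations in each of the 8 settings.

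**4. Cost of omitting race, behavioural outcome.** One follow-up, linear approximation. Suppose race explains a share m of outcome variance (assumed 2% to 10%), equally at baseline and follow-up. The plan's repeated-measures correlation is 0.8 (Protocol B.12).
- Residual variance given the baseline outcome: 1 − 0.8² = 0.36.
- Residual variance given baseline and race: (1−m) − (0.8−m)²/(1−m).
- m = 0.02: 0.98 − 0.78²/0.98 = 0.3592, so partial R² = 1 − 0.3592/0.36 = 0.2%.
- m = 0.10: 0.90 − 0.70²/0.90 = 0.3556, so partial R² = 1.2%.

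If a balanced stratum is left out, the true variance of the effect estimate is unchanged but its standard error is overstated by 1/s, with s = √(1 − partial R²). Power is then Φ(ncp − 1.96/s), with ncp = 2.802 for 80% power and 3.841 for the plan's stated 97%. Type I error is 2·P(Z > 1.96/s).

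| m | partial R² | loss from 80% | loss from 97% | type I error |
|---|---|---|---|---|
| 2% | 0.2% | 0.06 points | 0.02 points | 4.97% |
| 10% | 1.2% | 0.34 points | 0.08 points | 4.86% |

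Without the baseline outcome in the model (partial R² equal to m), the loss from 80% would be 0.6 to 3.1 points. That is not the planned model.

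**5. Cost of omitting race, STI outcome.** Logistic simulation with 720 men (900 × 80% retention), 120 per race per arm. Rectal chlamydia rates from Protocol B.6 (22.9 per 100 person-years in Black men, 6.7 in White men) are used as 12-month risks. The Latino risk is assumed low (6.7%), middle (14.8%) or high (22.9%). Power without and with race:

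| Odds ratio | Latino low | Latino middle | Latino high |
|---|---|---|---|
| 0.5 | 72.4% / 73.9% | 81.3% / 82.1% | 86.6% / 87.3% |
| 0.6 | 48.3% / 50.3% | 57.9% / 59.0% | 63.5% / 64.9% |
| 1 (null) | 4.4% / 5.0% | 4.4% / 4.9% | 4.4% / 4.9% |

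The gain is 0.7 to 2.0 points. This model leaves out baseline STI and site, which the plan includes and which may carry part of the race information. It also uses rectal chlamydia alone, while the endpoint is joint gonorrhoea/chlamydia at two anatomical sites.

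**The case against.** The strongest reply is that the sentence containing the test rule also admits variables already known to predict the outcome, whatever the baseline test shows. A reader might infer that prognostic variables are usually left out unless they happen to be imbalanced, and that much power is lost. The documents do not support that: any variable that could have been pre-specified as prognostic can already enter by the prior-research route.

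The same reply covers race. Protocol B.6 itself reports STI rates that differ by race, Protocol B.2 cites the team's own work on racial disparities in HIV risk, and the power section expects adjustment for the blocking. Race looks intended but not named. This stands, and it limits the point to what the text fails to require.

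A sponsor might also say that the adjusted analyses are secondary. That does not stand, because the single group effect is tested with all included covariates.

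Finally, a reader might infer that the open list inflates false positives. In a null simulation with assumed effects (4,000 runs, 720 men, ten covariates of which five are prognostic), reporting the best of four covariate sets gave 7.1%. That requires choosing the model after seeing results, and nothing in the documents says this is planned. It is a reason to close the list, not evidence of inflation.

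**Conclusion.** The point holds as a gap in specification and a poor selection rule, of modest severity. The text fixes only the baseline outcome and site, lets chance imbalances into the primary model, and does not require a randomisation stratum. Confidence in this reading is high.

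Applied mechanically, the rule and the omission of race leave the test at or slightly below its nominal size. The power cost of omitting race is likely a few tenths of a point or less for the behavioural outcome, and at most about 1 to 2 points for STI in the simplified model. These sizes rest on assumed race effects, an assumed Latino risk and the plan's correlation of 0.8, and they apply only if race does not enter by the open wording. The main benefit of a change is a primary model that is fixed beforehand and matches the randomisation.

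**What to change.** In SAP C3 and Protocol B.11:

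1. Delete the rule that selects covariates by baseline significance. Report baseline balance descriptively.
2. For both primary outcomes, list the covariates: baseline value of the outcome, race/ethnicity and CBO/site as coded in the stratified randomisation, and a short named set of prognostic variables including age. This list replaces the two open phrases. State the level of site (clinic or city) and the stratum code for men enrolled through ads or at-home testing, which the documents do not give.
3. Treat models with further covariates as sensitivity analyses.
4. Keep the race-by-arm interaction as the separate Aim 3 test.

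No new data and no change in sample size are needed: age, race, site and the baseline outcomes are already collected. The change is not entirely free of process. SAP E3 requires IRB and NIDA approval before protocol changes are implemented. The documents also mention preliminary analysis of STI results and outcome reports to the DSMB from the study statistician. The list should therefore be settled by people blind to outcomes by arm, and dated before any comparison of arms.

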#### **PROCEDURES**

Participants will be recruited (1) from the HIV testing clinics and mobile testing units of our partner CBOs in Chicago, New York, and Atlanta, (2) from HIV testing at Hunter College and Emory University, (3) from athome HIV testing, (4) from street outreach efforts of university staff and interns, (5) using print, online, and

recorded ads, (6) by referral from ongoing studies and IRB-approved research participant registries at the university sites, (7) by referral from community partners who provide HIV testing, and (8) from Chicago Department of Public Health (CDPH) clinics. Eligible participants across all study sites will be offered the opportunity to visit Emory University, Hunter College, or Northwestern University to complete the baseline assessment and complete their first set of self-administered STI test kits. Regardless of recruitment source, prior to beginning the intervention, participants will still have the contact with an HIV testing counselor or study team member that is important for recruitment and retention. They will be randomly assigned into one of two study groups, either the KIU! intervention or an HIV knowledge control condition. They will be asked to complete online questionnaires (five questionnaires total, approximately 20 - 40 minutes each), complete an online intervention within 3 weeks, and maintain consistent online contact throughout the course of the study (a total of 12 months after enrolling). This research includes at-home urine tests and at-home self-administered rectal swabs for STIs. Both STI tests will be collected at pre- and post-intervention (12 month follow-up). Participants who test positive at baseline will be tested at 3 month and 6 month follow-up in addition to at the 12 month follow-up.

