The primary behavioral outcome will be the count of unprotected anal sex acts and the primary biomedical outcome will be STI incidence. Additional behavioral outcomes include: alcohol and drug use prior to sex, risky sex after drug use, condom errors, IMB Model factors, and receipt of an HIV test. Similar procedures and measures successfully used in the developmental study will be employed (study measures are described in Table 1). Assessments will be completed via the Internet using a Computer-Assisted Self Interview (CASI). We will administer knowledge/information based measures immediately post-intervention along with the measures of intervention acceptability and tolerability. Motivation, skills (i.e. partner sexual communication, correct condom use), and behavioral outcomes (i.e. number of insertive and receptive unprotected anal sex acts, condom errors) will be measured at all follow-up points. Whenever possible, we selected measures: (1) designed for high-risk YMSM to maximize sensitivity, (2) previously tested with diverse populations to minimize cultural bias, and (3) to maximize comparability to other studies in order to compare findings.

Table	e 1: Study measures.	
	Construct	Measure
	Administration Points	
Outcomes	Unprotected sex acts HIV testing, and substance use BL 3 6 12	The AIDS-Risk Behavior Assessment (ARBA) ^{191,192} has been used with YMSM ^{82,102,191} and assesses behaviors on a partner-by-partner level, starting with recent partners, as well as in the aggregate. Partners are classified as serious or casual and relationship duration is measured ⁹⁵ . Questions differentiate between insertive and receptive anal sex. The ARBA will also assess drug and alcohol use, and secondary outcomes of HIV testing behaviors.
Primary (STI incidence BL 3 6 12	CT and GC testing of urine and rectal samples using the FDA cleared Gen-Probe APTIMA Combo 2 Assay. All participants will be tested at baseline and 12 month follow-up. Participants who test positive at baseline will also be tested at 3 month and 6 month follow-ups

	HIV Information	*The brief HIV/AIDS Knowledge questionnaire assess knowledge of transmission and
	BL 3 6 12	prevention ¹⁹³ . It has strong internal consistency, test-retest stability ¹⁹³ , and has been
		used successfully with young adults ¹⁹⁴ . A total correct score will be used in analyses.
	Motivation & Behavioral	*HIV/AIDS Motivation and Behavioral Skills ¹⁹⁵ assesses: Motivation (e.g. intentions to

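### The second time strategy makes baseline an outcome row while baseline is also a covariate; followed literally, it shrinks the group effect (to 0.75 of its size in the simplest linear model)

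*SAP*

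**What the plan says.** SAP section C3 (Data analysis plan) and Protocol B.11 (RCT Analytic Plan) carry the same text on this point. They list four assessment points for the trial outcomes: baseline, 3, 6 and 12 months. On the rows of the analysis they say "the primary analysis will utilize all follow-up points by fitting mixed effect regression models". On baseline they say "The baseline value of the outcome and other required covariates at baseline will be included as additional independent variables". A random intercept is included.

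Time is handled in two ways. It is first categorical. Then: "A second strategy will start with estimating a single slope reflecting average change across all 4 time points", with a quadratic term added if significant. Further, "Random effects for time variables, reflecting individual variations in time trends, will be included in addition to random intercepts, if significant".

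After both strategies comes the test: "A single effect of group will test the intervention effect averaged across all time points". The paragraph ends with "Addition of interaction terms between time and intervention group will provide a test for comparing time trends in change scores between groups".

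No sentence removes the baseline covariate for the second strategy, sets the arms equal at baseline, or says which strategy supplies the primary estimate.

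**The concern.** The sentence on follow-up points and the baseline covariate fit together: three outcome rows per participant, adjusted for baseline. The second strategy does not fit with them. A slope over four points needs baseline as an outcome row. The immediate post-intervention assessment cannot be the fourth point, because Protocol B.10(d) uses it for knowledge and acceptability, and the measures table lists the primary behavioral outcome at baseline, 3, 6 and 12 months.

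Taken literally, the same baseline value then sits on both sides of the model. The arms do not differ at baseline except by chance, and adjustment for baseline removes even that. A row that cannot show an effect is therefore averaged into the group coefficient. Two analysts working from the same plan could report different rate ratios for the primary behavioral outcome, one of them too close to 1.

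**Working it through.** The documents print no group effect under either strategy, so there is no figure of the plan's own to reproduce. The nearest, 97% power at ERR 0.89 (SAP A.5), is not in dispute here.

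**Inputs.** Four assessment points, three after randomization (SAP C3). Rate ratios 0.89 (SAP A.5) and 0.56 (pilot, Protocol B.3, Table 1). Correlation between repeated measures 0.8 and retention 80% (SAP A.5). Other values are marked as assumed.

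**Step 1: linear model, random intercept, complete data.** Every participant has the same visit times, so the group coefficient equals that from regressing each participant's mean outcome on group and baseline.

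- Three rows: the outcome is F, the mean of the 3-, 6- and 12-month values. Call the group coefficient d.
- Four rows: the outcome is 0.25 × baseline + 0.75 × F. Regressing baseline on group and baseline gives a group coefficient of 0 and no residual. The group coefficient is therefore 0.25 × 0 + 0.75 × d = 0.75 d.
- The residuals are also multiplied by 0.75, so the standard error is too, and estimate/SE does not change.

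Model fits with 20,000 per arm confirm this:

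| Correlation | Three rows (SE) | Four rows (SE) | Ratio | z ratio |
|---|---|---|---|---|
| 0.8 | 0.1453 (0.0048) | 0.1090 (0.0036) | 0.750 | 1.00 |
| 0.4 | 0.1943 (0.0066) | 0.1458 (0.0050) | 0.750 | 1.00 |

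**Step 2: the same factor on the log scale.**

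- 0.89^0.75 = exp(0.75 × −0.1165) = 0.916, so an 11% reduction would read as 8.4%.
- 0.56^0.75 = exp(0.75 × −0.5798) = 0.647, so a 44% reduction would read as about 35%.

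**Step 3: departures from the simple case.** These rest on values that the documents do not give.

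- Dropout, linear random intercept, assuming 20% are lost right after baseline: factor 0.68 at correlation 0.8 and 0.69 at 0.4, z ratio 0.99 to 1.00. Participants who are lost still contribute their baseline row, which carries no effect.
- Random time slope, complete data: factor 0.54 and z ratio 0.81 for data with constant correlation 0.8. Assuming slope variances from 0.05 to 1.0 per year squared and correlations of 0.5 and 0.8, the factor is 0.43 to 0.57 and the z ratio 0.79 to 0.83. A random slope makes later visits noisier in the model, so the fit leans more on the early rows, baseline included.
- Poisson random intercept, 450 per arm, complete data, assuming baseline and control follow-up means of 6.2 (the pilot's 3-month control mean as a stand-in), latent SD 1.2 and latent correlation 0.5 or 0.8: four-row fits give 0.916 to 0.921 for a true 0.89 and 0.66 to 0.67 for a true 0.56. Three-row fits give 0.889 to 0.893 and 0.558 to 0.562. Assuming random loss of 10, 15 and 20% by 3, 6 and 12 months, the four-row fits give 0.923 to 0.930 and 0.68 to 0.70.

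**Step 4: a sound four-row alternative.** Drop the baseline covariate, give the arms a common baseline mean, and estimate group by post-baseline time. In linear fits at correlations 0.5 and 0.8 this matches the three-row random-intercept estimate within 0.002. The common mean matters for precision. With unit variances and correlation r, the variance of F adjusted for baseline is (1 + 2r)/3 − r², and that of the change score is 4(1 − r)/3.

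- r = 0.5: 0.667/0.417 = 1.60, so the change-score SE is 26% larger.
- r = 0.8: 0.267/0.227 = 1.18, so it is 8% larger.

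**The case against.** The strongest reply is that the plan already names the primary rows. The follow-up sentence governs, categorical time comes first, and the slope is a second way to describe time. Nothing hands the primary test to it. After that sentence, an average over all time points can be read as all follow-up points, and a careful statistician would fit three rows.

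Most of this stands. The three-row model is sound, and dilution arises only if the second strategy is carried out as worded. What does not stand is that the text settles the matter. The sentence on the group effect follows both strategies and is not limited to the first, and the closing mention of change scores leaves a four-row model open. A prespecified plan should not rely on the analyst to correct it silently.

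Three stronger readings are tempting and not supported:

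- That the primary result will be diluted. The documents show an ambiguity, not a commitment to the faulty combination.
- That power is lost throughout. In the linear random-intercept model with complete data the test is unchanged. It weakens with a random slope. No power or coverage figure is claimed for the count model.
- That the STI endpoint is biased because the follow-up wording does not match its schedule. The schedule is explicit: everyone is tested at baseline and 12 months, and "Participants who test positive at baseline will also be tested at 3 month and 6 month follow-ups". That extra testing depends on baseline status, which is a model covariate. No bias has been shown, and the role of the retests is a separate question.

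**Conclusion.** The point holds as a conflict in wording, limited to the second time strategy and the unspecified averaging in the group test. Followed literally, the strategy multiplies the group estimate and its standard error by 0.75 in a linear random-intercept model with complete data and a constant follow-up effect. That factor is algebra and needs no assumed variance. Its translation to rate ratios (0.89 to 0.916, 0.56 to 0.647) applies the linear factor on the log scale; the Poisson fits give similar or slightly larger dilution under assumed means and variances. The figures for dropout and random slopes show direction and rough size only. The error is toward no effect, so it would understate the intervention. It should be fixed before analysis.

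**What to change.** In SAP C3 and Protocol B.11, replace the reference to four time points in the second strategy with the three follow-up points (3, 6 and 12 months). State that baseline enters only as a covariate, and that the single group effect averages those three points.

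If four outcome rows are preferred, drop the baseline covariate, constrain the arms to a common baseline mean, and take the effect from the group-by-post-baseline terms. The constraint must be written down, since without it the analysis becomes a change-score comparison with the loss of precision shown above. A single linear time-by-group slope does not give these terms.

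Either version is sound; the plan should name one. The cost is a few sentences in two places, with no change to data collection, visits or sample size.
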